6. STUDY PROCEDURES

6.1. Screening and Enrollment

Informed consent must be obtained prior to performance of any study-specific tests or evaluations. Screening should occur within 28 days and not exceed 31 days prior to randomization. Subjects will undergo the following evaluations to determine their eligibility for study participation:

- Recording of demographic data and relevant medical history in the EDC;
- Recording of all prior medications and treatments for HS from diagnosis to Screening in the EDC;
- Recording of all other concomitant medications on the Screening day(s) in the EDC, including alcohol intake, recreational drug use, non-prescription medications, herbal preparations or special diets;
- A physical examination will be performed (see [Section 7.2.1](#)); body weight and height will be measured;
- Vital signs will be obtained as detailed in [Section 7.2.1](#); temperature, sitting blood pressure, and heart rate will be measured after at least 3 minutes of rest;
- Serum pregnancy test (in women of childbearing potential);
- Virology assessments as detailed in [Section 7.2.2](#), unless done within 6 weeks prior to Screening;
- Tuberculosis exclusion based on interferon γ release assay (IGRA);
- 12-lead ECG to exclude any clinically significant findings;
- Serum chemistry and hematology tests according to [Section 7.2.2](#);
- A urine sample will be collected for urinalysis (see [Section 7.2.2](#));
- The anatomic location and number of HS inflammatory nodules, abscesses, fistulae, and hypertrophic scars and the Hurley Stage of HS will be recorded;
- Any pre-treatment adverse events (occurring during the Screening visit) will be recorded.

Results from certain tests that have been performed prior to Screening may be used to determine study eligibility if these tests were performed as part of the practice of medicine and were done whether or not study entry was contemplated, such as for diagnosis or treatment of the subject's condition. Results from the prior tests must be recorded in the EDC.

After all Screening procedures have been completed and the subject satisfies all eligibility criteria:

- The study schedule will be discussed with the subject and the schedule will be provided to the subject to ensure compliance with the study visits.

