Data collected at all visits will be included in the data listings with visit presented as reported by the site.

C. Missing Data

Imputation for Efficacy variables:

The approaches listed below will be used for handling missing data:

- Non-responder imputation (NRI): Subjects who have missing data at the time point of interest are treated as though they did not respond to the treatment.
- Last Observation Carried Forward (LOCF): The LOCF analyses will use
 the last observed non-missing evaluation (last completed non-missing
 evaluation, from composite endpoint) from the previous visit within the
 particular period for efficacy measures assessed to impute missing data at
 later visits in the same period. Baseline efficacy evaluations will not be

carried forward. LOCF will be the primary approach in the analysis of continuous variable.

- Observed case (OC): Missing data are not imputed. Only subjects with available data at the given time point are considered.
- Multiple Imputation (MI) Markov Chain Monte Carlo (MCMC) imputation: Using multiple imputation methodology, missing data in Period 1 are imputed based on the MCMC method, please see Section VIII D for details

The following table depicts which missing data handling approaches should be used based on variable priority (primary, secondary, other) and variable type (binary, continuous).

		Missing Data Handling Approach					
Endpoints	Variable Type	NRI	MI	LOCF	ос		
Primary Efficacy	Binary	P	SEN	SEN			
Primary Efficacy (COVID-19)	Binary	P		SEN			
Secondary/ Other Efficacy	Binary	P	SEN				
(selected ones only, see Page 47)	Continuous			P1	SEN		

P=Primary method, SEN=Sensitivity method

Imputation for AE and Concomitant Medication Start Dates:

For analyses of AEs and concomitant medication usage, a complete date must be established in order to correctly identify the AE or medication as occurring during treatment or not. For purposes of imputing missing components of partially-reported start and stop dates for AEs and for medication use, the algorithms listed below will be followed. Start and stop dates of AEs or concomitant medication will be displayed as reported in the subject data listings (i.e., no imputed values will be displayed in data listings).

Partial AE and concomitant medication start dates will be imputed as follows:

- If year is missing, no imputation will be performed.

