- If both day and month of the start date are missing, the day and month will be imputed with the day and month of the first study dose date if the year is equal to the year of first dose. Otherwise, the month and day is imputed as the first day of the year (01 Jan).

¹⁼For selected endpoints

 If only day is missing, and if the year and month are equal to the first dose date, the day will be imputed as day of the first dose date. Otherwise, the day will be imputed as "01".

D. Multiple Study Centers

No adjustment for stratification by the study centers is planned. However, centers will be grouped by geographic region and a subgroup analysis will be conducted to determine if region impacts the primary endpoint.

E. Covariate Adjustment in Primary Analysis

Continuous variables of the secondary/other efficacy endpoints, change from Baseline to Week 12 in the Sartorius score, modified Sartorius score, IHS4 score, HS-PGA, inflammatory and non-inflammatory nodule count, abscess count, draining, non-draining and total fistula count, total AN count, SF-36 v2 (domains and component scores) and EQ-5D-5L (visual analogue scale and index), HiSQOL, DLQI, and WPAI:SHP will be analyzed using a mixed effects model for repeated measures. This model will include treatment group, visit, treatment-by-visit interaction, and randomization strata (Hurley Stage II or Hurley Stage III, anti-TNF drug use or anti-TNF drug naive) as factors, and corresponding baseline as covariate.

Change from Baseline to Week 12 in WPAI:SHP will be analyzed using an ANCOVA model which includes treatment group, randomization strata (Hurley Stage II or Hurley Stage III, anti-TNF drug use or anti-TNF drug naive) as factors, and corresponding baseline as covariate.

F. Sample Size Reassessment

No sample size reassessment is planned.

G. Interim Analyses or Timing of Analyses

No interim analyses planned.

H. Test Sizes

All confidence intervals will be two-sided with 95% coverage.

I. Multiple Comparisons/Multiplicity

For the primary efficacy endpoint testing, the avacopan 30 mg vs. placebo in HiSCR (H_{11}) and the avacopan 10 mg vs. placebo in HiSCR (H_{12}), a hierarchical procedure will be used to control the overall α at 0.05 level.

That is if H_{11} is rejected at a 2-sided alpha level of 0.05, then the H_{12} will be tested at 2-sided alpha level of 0.05.

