- Ethnicity (Hispanic or Latino, Not Hispanic or Latino, Not Reported)
- Race (White, Black or African American, Native Hawaiian or Other Pacific Islander, Asian, American Indian or Alaskan Native, Other, Not Reported)
- Height (cm)
- Weight (kg)
- BMI (kg/m²)
- Hurley Stage of HS
- HS disease duration (from time of diagnosis)
- HS lesion counts:
 - Number of AN counts
 - Number of inflammatory nodules

- Number of abscesses
- Number of draining fistulae
- Number of AN count categories: <5, 5-10, ≥10
- Number of hypertrophic scars
- Sartorius and modified Sartorius scores
- IHS4 score
- HS-PGA
- Anatomic location of HS
- Subject's global assessment of skin pain NRS
- Previous systemic HS treatment (includes TNF inhibitor use but excludes antibiotic use)
- Previous TNF inhibitor use
- Previous antibiotic treatment for HS
- Prior surgery for HS
- SF-36 v2
- EQ-5D-5L index
- HiSQOL index
- DLQI index
- Health Economics WPAI:SHP

A listing of demographic and baseline information will be provided.

The stratification factor values as collected in the electronic case report forms will be used for the summaries of baseline characteristics.

Medical History and Concurrent Procedures

The Medical Dictionary for Regulatory Activities (MedDRA; Version 21.1) will be used to code all medical history terms or concurrent procedures to a System Organ Class (SOC) and Preferred Term (PT). Medical History/concurrent procedures will be summarized by SOC in alphabetical order, preferred term in alphabetical order, and by treatment group. Subjects reporting more than one PT within a SOC will be counted only once for that SOC.

All medical history and concurrent procedures will be provided in a listing separately.

Prior and Concomitant Medications

Prior medications are defined as any medication taken prior to the first dose of blind study medication. Concomitant medications are defined as any medication taken on or after the first dose of blind study medication. A medication is classified as both prior and concomitant if it started prior to the first dose of blind study medication date and continued into the treatment period.

Prior/concomitant medications will be coded to therapeutic class and preferred term using the World Health Organization Drug Dictionary (WHO-DD), Version September 2018.

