Proportion of subjects with a LOR in Period 2 is calculated as those subjects having AN Counts in Period 2 $> 0.5 \times$ (Baseline AN counts —Week 12 AN counts) divided by the total number of subjects in each treatment group in Period 2.

12) Time to LOR during Period 2.

For subjects with LOR, time to LOR (days) = date of LOR – date of the first dose of study drug in Period 2 + 1; For Subjects without LOR or lost follow-up, subjects will be censored at the date of the last assessment of number of HS lesions, i.e., time to LOR (days) = date of last assessment of number of HS lesions – date of the first dose of study drug in Period 2 + 1.

 Proportion of subjects who received add-on antibiotic or other therapy for HS during Period 1 and Period 2 separately.

Add-on antibiotic or other therapies for HS are captured in the Concomitant Medication CRFs.

Proportion of subjects who received add-on antibiotic or other therapy will be calculated as those subjects who received add-on antibiotic or other therapy documented in the CM CRF post baseline divided by the total number of subjects in each treatment group in the safety population.

14) Proportion of subjects who start disallowed opioid pain therapy during Period 1 and Period 2 separately.

Oral and transdermal opioid analgesics (except for tramadol) for any reason are disallowed. Disallowed opioid pain therapy are captured in the Concomitant Medication (CM) CRFs.

Proportion of subjects who start disallowed opioid pain therapy will be calculated as those subjects who start disallowed opioid pain therapy documented in the CM CRF post baseline divided by the total number of subjects in each treatment group in safety population.

15) Proportion of subjects who undergo lesion intervention due to HS during Period 1 and Period 2 separately.

Lesion intervention due to HS is collected in AE and Concurrent Procedures CRFs.

Only two types of interventions are allowed: injection with intralesional triamcinolone acetonide suspension (intralesional Kenalog® rescue injections, i.e., triamcinolone acetonide, 10 mg total maximum per subject within a period no longer than 1 week) and incision and drainage. Any disallowed lesions interventions due to HS other than the two types described above will also be counted as "Lesion intervention due to HS" and will be recorded as major (=CSR reportable) protocol deviation.

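### SAP VI.C dates partial AE and medication starts to the first dose without checking the stop date, so a record that ended before dosing can be given a start after its own stop (wrong as written, minor)

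*SAP*

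**What the plan says.** SAP VI.C, under the heading on AE and concomitant medication start dates, gives the purpose of the imputation: "a complete date must be established in order to correctly identify the AE or medication as occurring during treatment or not". It announces rules for "partially-reported start and stop dates for AEs and for medication use, the algorithms listed below will be followed", but only start-date rules follow:

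- Year missing: no imputation.
- Day and month missing: if the year is that of first dose, "the day and month will be imputed with the day and month of the first study dose date"; otherwise 1 January.
- Only the day missing: "if the year and month are equal to the first dose date, the day will be imputed as day of the first dose date"; in any other month, it becomes 01.

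No stop-date rule is given, and none of the three rules refers to a stop date. The same section states that "no imputed values will be displayed in data listings".

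These sections use the resulting date or status:

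- SAP VII.C: "Concomitant medications are defined as any medication taken on or after the first dose of blind study medication".
- SAP IX.A: a Period 1 TEAE is one occurring after the first dose in Period 1 and before the first dose in Period 2.
- SAP VIII.B, item 14: the disallowed-opioid numerator is "those subjects who start disallowed opioid pain therapy documented in the CM CRF post baseline". Item 13 counts add-on antibiotic or other therapy in the same way.
- SAP VIII.C: efficacy data after the start of a major disallowed treatment are dropped, and the subject becomes a non-responder on categorical endpoints.
- SAP VIII.D, sensitivity analysis 2: add-on antibiotics, anti-TNF or other systemic HS treatment lead to non-response.

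Pre-dose records are collected by design. Protocol 6.1 says "Any pre-treatment adverse events (occurring during the Screening visit) will be recorded", Protocol 6.2 repeats this on Day 1 for the time since Screening, and HS medications are recorded back to diagnosis.

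**The concern.** Moving an incomplete start to the first dose is the usual cautious choice when nothing shows that the event was over by then. When the record carries a stop date before first dose, it does show this. The rule then overrides recorded information and produces an impossible sequence, with the start after the stop. Because listings show reported dates only, the contradiction would not appear there.

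The safety consequence is that screening events can enter the Period 1 TEAE tables, which serve a primary objective. For medications, a permitted treatment that finished before the study can be counted as concomitant, add-on or disallowed. Through SAP VIII.C or VIII.D it could also turn a subject into a non-responder.

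**Working it through.** The documents give no figure for this, so there is none to reproduce. The check applies the rules as written to example records and then measures how wide the exposed window is.

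**Literal application.** Illustrative first dose: 20 September 2019.

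| Reported start | Stop | Imputed start (SAP VI.C) | After own stop? | With a stop-date check |
|---|---|---|---|---|
| day unknown, Sep 2019 | 10 Sep 2019 | 20 Sep 2019 | yes, by 10 days | 01 Sep 2019, pre-treatment |
| day and month unknown, 2019 | 15 Mar 2019 | 20 Sep 2019 | yes, by 189 days | 01 Jan 2019, prior |
| day unknown, Aug 2019 | 30 Aug 2019 | 01 Aug 2019 | no | unchanged |

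For row 2, 15 March to 20 September is 16 + 30 + 31 + 30 + 31 + 31 + 20 = 189 days. Row 3 shows that the fault arises only where the known part of the start matches the first-dose date.

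**Exposed window, day-only rule.** Input: screening of 28 days, at most 31 (Protocol 6.1). Assumption: first-dose dates spread evenly over a 365-day year. For first dose on day d of a month and a window of W days, min(d − 1, W) screening days lie in the same month. Summing over d:

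- W = 28: 462 for a 31-day month, 434 for a 30-day month, 378 for a 28-day month. Total 7 × 462 + 4 × 434 + 378 = 5,348 of 365 × 28 = 10,220 days, or 52%.
- W = 31: 465, 435 and 378. Total 7 × 465 + 4 × 435 + 378 = 5,373 of 365 × 31 = 11,315 days, or 47%.

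So about half of screening days lie where the day-only rule moves a start to the first-dose day.

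**Opioids.** Exclusion 10 (Protocol 4.2) reaches back 14 days before Day 1, so an earlier, completed course is compatible with entry. In a 30-day month, among courses starting 15 to 28 days before dosing, the share starting in the first-dose month is the sum over d of max(0, min(d − 1, 28) − 14), divided by 30 × 14. That is (1 + 2 + … + 14) + 14 = 119 of 420, or 28%.

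**Route to non-response.** Two exclusions in Protocol 4.2 matter. Exclusion 9 bars systemic HS medicines, other than the permitted antibiotic regimens, within at least 30 days or 5 half-lives of the last dose. Exclusion 5 requires anti-TNF to have been stopped more than 12 weeks (84 days) before Day 1. A medicine that both started and ended in the first-dose month before dosing was last taken about 30 days or less before Day 1, so an eligible subject should rarely have such a record.

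The day-and-month rule is different. If row 2 is a completed anti-TNF course, 189 days exceeds 84, so exclusion 5 permits it. SAP VI.C nevertheless dates its start to Day 1. Read literally, SAP VIII.C would then drop every later efficacy assessment and count Week 12 HiSCR as non-response. A completed antibiotic course could become add-on therapy in the same way. Prior courses are expected, because inclusion 4 is built on antibiotic failure.

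**The case against.** The strongest case against is that other text limits the damage.

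- **AEs.** The TEAE definition requires occurrence after the first dose, while the imputed date equals the first-dose date. Protocol 7.2.3 also treats AEs reported before dosing as pre-treatment. This stands in part. The SAP does not say how a date-only Day 1 event is classed, and a strict reading would also lose genuine Day 1 events. SAP I.A gives SAP definitions precedence, and the pre-treatment rule is not carried into VI.C.
- **Medications.** A medicine stopped before first dose was not taken on or after it, so a programmer who tests the stop date gets the right answer. That stands, but the SAP does not instruct it.
- **Opioid count.** Item 14 counts post-baseline starts, and the SAP visit windows place Day 1 in Baseline. Whether an imputed Day 1 start counts is unsettled.
- **Reviews.** Rescue medication and disallowed pain therapy are reviewed before lock, and PP1 medications are classified before blind break. These may catch some medication cases. None covers AEs.
- **Direction.** The rule is the same in all arms, AE tables count a subject once per term, and non-responder imputation for missing data is untouched. This stands.

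A reader might infer two stronger conclusions. One is that recent medicines commonly become non-responder events; the exclusions largely close that route when only the day is missing. The other is a fixed percentage of misclassified screening AEs. With assumed durations of 3 to 10 days and a 30-day month, the share of day-missing screening AEs that start in the first-dose month and end before dosing runs from about 23% (fixed 10 days: 189 of 840 combinations) to 44% (exponential, mean 3 days). The documents give neither durations nor a count of partial dates, so no single figure is supported.

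**Conclusion.** Wrong as written, minor. The rule gives a demonstrably false date to any record with a partial start matching the first-dose month (or year, if the month is missing) and a stop known to precede first dose. That date can feed the treatment-emergent, concomitant, add-on and disallowed-therapy classifications.

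The exposed window is not marginal: 47% to 52% of screening days under the day-only rule, and potentially the whole pre-dose part of the first-dose year when the month is also missing. The number of affected records cannot be computed from the documents and could be zero. Being arm-neutral, the error would mainly add noise. An effect on the primary endpoint is possible, chiefly through the day-and-month-missing rule, but nothing in the documents shows that it would be material.

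Where the stop date is missing, or falls on or after first dose, imputing to the first dose remains a reasonable conservative choice and is not criticised here.

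**What to change.** Add to both start-date rules in SAP VI.C:

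*If the complete or partial stop date shows that the event or medication ended before the first dose, do not impute to the first-dose date; impute the start day as 01 of the known month, or 01 Jan if the month is missing, and classify the record as pre-treatment/prior. An imputed start date may never be later than the stop date.*

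In the same edit, either supply the stop-date algorithm that the section announces or delete the mention of it, and state whether a start imputed to the first-dose date counts as after first dose for TEAEs and as post baseline for items 13 and 14.

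The cost is a short SAP edit and one condition in the date program. No new data are needed.
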